### Programming Note: Repeat table for Non-Inflammatory Lesions:

Table 14.2.2.2 Non-Inflammatory Lesion Counts by Study Visit (Face Only) Safety Population

Protocol Number: NI-AC303

_		SB204 Experienced (N=XXX)			SB204 Naïve (N=XXX)		
	·	Count	Absolute	Percent	Count	Absolute	Percent Change
			Change	Change		Change	from Baseline
			from	from		from	
Visit	Statistic		Baseline	Baseline		Baseline	
Baseline	N	XX			XX		
	Mean	XX.X			XX.X		
	SD	XX,XX			XX,XX		
	Median	XX			XX		
	Min. to Max.	XX to XX			XX to XX		
Week 4	N	XX	XX	XX	XX	XX	XX
	Mean	XX.X	XX.X	XX.X	XX.X	XX.X	XX.X
	SD	XX,XX	XX,XX	XX,XX	XX,XX	XX,XX	XX,XX
	Median	XX	XX,X	XX,X	XX	XX,X	XX,X
	Min. to Max.	XX to XX	XX to XX	XX to XX	XX to XX	XX to XX	XX to XX
Week 12	N	XX	XX	XX	XX	XX	XX
	Mean	XX.X	XX.X	XX.X	XX.X	XX.X	XX.X
	SD	XX,XX	XX,XX	XX,XX	XX,XX	XX,XX	XX,XX
	Median	XX	XX,X	XX,X	XX	XX,X	XX,X
	Min. to Max.	XX to XX	XX to XX	XX to XX	XX to XX	XX to XX	XX to XX

Source: Listing xx.x.x.x, Program: xxxxx.sas, Output: T xx.x x x xxxx.rtf, Generated on: DDMMMYYYY HH:MM

### Programming Note: Repeat table for Non-Inflammatory Lesions:

Table 14.2.3.2 Non-Inflammatory Lesion Counts (Face Only) by Prior Treatment and Study Visit Safety Population

Protocol Number: NI-AC303

Table 14.3.1.1

Cutaneous Tolerability Evaluation - Erythema - Summarized by Study Visit (Face Only)

Safety Population

	SB204
Study Visit	(N=XXX)
Baseline	
0 - None	xx (xx.x)
1 - Mild	xx (xx.x)
2 - Moderate	xx (xx.x)
3 - Severe	xx (xx.x)
Missing	xx (xx.x)
Week 4	
0 - None	xx (xx.x)
1 - Mild	xx (xx.x)
2 - Moderate	xx (xx.x)
3 - Severe	xx (xx.x)
Missing	xx (xx.x)
Week 12	
0 - None	xx (xx.x)
1 - Mild	xx (xx.x)
2 - Moderate	xx (xx.x)
3 - Severe	xx (xx.x)
Missing	xx (xx.x)
Week 24	
0 - None	xx (xx.x)
1 - Mild	xx (xx.x)
2 - Moderate	xx (xx.x)
3 - Severe	xx (xx.x)
Missing	xx (xx.x)
Week 36	
0 - None	xx (xx.x)
1 - Mild	xx (xx.x)
2 - Moderate	xx (xx.x)
3 - Severe	xx (xx.x)
Missing	xx (xx.x)
Week 40\ET	
0 - None	xx (xx.x)
1 - Mild	xx (xx.x)
2 - Moderate	xx (xx.x)
3 - Severe	xx (xx.x)
Missing	xx (xx.x)

Note: Baseline is the Week 12 assessment from the previous study (NI-AC301 or NI-AC302).

Source: Listing xx.x.x.x, Program: xxxxx.sas, Output: T\_xx.x\_x\_x\_xxxx.rtf, Generated on: DDMMMYYYY HH:MM

Protocol Number: NI-AC303

#### Using shell 14.3.1.1, repeat table for the following:

Table 14.3.1.2 Cutaneous Tolerability Evaluation - Scaling - Summarized by Study Visit Safety Population

Table 14.3.1.3 Cutaneous Tolerability Evaluation - Dryness - Summarized by Study Visit Safety Population

Table 14.3.1.4 Cutaneous Tolerability Evaluation - Pruritus - Summarized by Study Visit Safety Population

Table 14.3.1.5 Cutaneous Tolerability Evaluation - Burning/Stinging - Summarized by Study Visit Safety Population

Protocol Number: NI-AC303

Table 14.3.2.1

Shift from Baseline in Cutaneous Tolerability Evaluation - Erythema, by Study Visit (Face Only)

Safety Population

Study Visit /		Cutaneou	s Tolerability Score	at Baseline	
Cutaneous Tolerability					
Score	0 - None	1 - Mild	2 - Moderate	3 - Severe	Missing
Week 4	,	,	,	,	,
0 - None	xx (xx.x)	xx (xx.x)	xx (xx.x)	xx (xx.x)	xx (xx.x)
1 - Mild	xx (xx.x)	xx (xx.x)	xx (xx.x)	xx (xx.x)	xx (xx.x)
2 - Moderate	xx (xx.x)	xx (xx.x)	xx (xx.x)	xx (xx.x)	xx (xx.x)
3 - Severe	xx (xx.x)	xx (xx.x)	xx (xx.x)	xx (xx.x)	xx (xx.x)
Missing	xx (xx.x)	xx (xx.x)	xx (xx.x)	xx (xx.x)	xx (xx.x)
Week 12					
0 - None	xx (xx.x)	xx (xx.x)	xx (xx.x)	xx (xx.x)	xx (xx.x)
1 - Mild	xx (xx.x)	xx (xx.x)	xx (xx.x)	xx (xx.x)	xx (xx.x)
2 - Moderate	xx (xx.x)	xx (xx.x)	xx (xx.x)	xx (xx.x)	xx (xx.x)
3 - Severe	xx (xx.x)	xx (xx.x)	xx (xx.x)	xx (xx.x)	xx (xx.x)
Missing	xx (xx.x)	xx (xx.x)	xx (xx.x)	xx (xx.x)	xx (xx.x)
Week 24					
0 - None	xx (xx.x)	xx (xx.x)	xx (xx.x)	xx (xx.x)	xx (xx.x)
1 - Mild	xx (xx.x)	xx (xx.x)	xx (xx.x)	xx (xx.x)	xx (xx.x)
2 - Moderate	xx (xx.x)	xx (xx.x)	xx (xx.x)	xx (xx.x)	xx (xx.x)
3 - Severe	xx (xx.x)	xx (xx.x)	xx (xx.x)	xx (xx.x)	xx (xx.x)
Missing	xx (xx.x)	xx (xx.x)	xx (xx.x)	xx (xx.x)	xx (xx.x)
Week 36					
0 - None	xx (xx.x)	xx (xx.x)	xx (xx.x)	xx (xx.x)	xx (xx.x)
1 - Mild	xx (xx.x)	xx (xx.x)	xx (xx.x)	xx (xx.x)	xx (xx.x)
2 - Moderate	xx (xx.x)	xx (xx.x)	xx (xx.x)	xx (xx.x)	xx (xx.x)
3 - Severe	xx (xx.x)	xx (xx.x)	xx (xx.x)	xx (xx.x)	xx (xx.x)
Missing	xx (xx.x)	xx (xx.x)	xx (xx.x)	xx (xx.x)	xx (xx.x)
Week 40					
0 - None	xx (xx.x)	xx (xx.x)	xx (xx.x)	xx (xx.x)	xx (xx.x)
1 - Mild	xx (xx.x)	xx (xx.x)	xx (xx.x)	xx (xx.x)	xx (xx.x)
2 - Moderate	xx (xx.x)	xx (xx.x)	xx (xx.x)	xx (xx.x)	xx (xx.x)
3 - Severe	xx (xx.x)	xx (xx.x)	xx (xx.x)	xx (xx.x)	xx (xx.x)
Missing	xx (xx.x)	xx (xx.x)	xx (xx.x)	xx (xx.x)	xx (xx.x)

Note: Baseline is the Week 12 assessment from the previous study (NI-AC301 or NI-AC302).

Source: Listing xx.x.x.x, Program: xxxxx.sas, Output: T\_xx.x\_x\_xxxx.rtf, Generated on: DDMMMYYYY HH:MM

Protocol Number: NI-AC303

Using shell 14.3.2.1, Repeat table for the following:

Table 14.3.2.2 Shift from Baseline in Cutaneous Tolerability Evaluation - Scaling - Summarized Continuously by Study Visit Safety Population

Table 14.3.2.3 Shift from Baseline in Cutaneous Tolerability Evaluation - Dryness - Summarized Continuously by Study Visit Safety Population

Table 14.3.2.4 Shift from Baseline in Cutaneous Tolerability Evaluation - Pruritus - Summarized Continuously by Study Visit Safety Population

Table 14.3.2.5 Shift from Baseline in Cutaneous Tolerability Evaluation - Burning/Stinging - Summarized Continuously by Study Visit Safety Population

Protocol Number: NI-AC303

Table 14.3.3.1

Treatment Emergent Adverse Events (TEAE) Overview
Safety Population

Number of Subjects with	SB204 Experienced (N=XXX)	SB204 Naïve (N=XXX)	Overall (N=XXX)
Any TEAE	xx (xx.x)	xx (xx.x)	xx (xx.x)
Number of TEAEs	xx	xx	
Treatment-Related TEAE Number of Treatment-Related TEAEs	xx (xx.x)	xx (xx.x)	xx (xx.x)
	xx	xx	xx
TEAE Leading to Treatment Modification	xx (xx.x)	xx (xx.x)	xx (xx.x)
Number of TEAE Leading to Treatment Modification	xx	xx	xx
Treatment-Related TEAE Leading to Treatment Modification Number of TRTEAE Leading to Treatment Modification	xx (xx.x)	xx (xx.x)	xx (xx.x)
	xx	xx	xx
TEAE Leading to Treatment Discontinuation	xx (xx.x)	xx (xx.x)	xx (xx.x)
Number of TEAE Leading to Treatment Discontinuation	xx	xx	xx
Treatment-Related TEAE Leading to Treatment Discontinuation Number of TRTEAE Leading to Treatment Discontinuation	xx (xx.x)	xx (xx.x)	xx (xx.x)
	xx	xx	xx
Serious TEAE	xx (xx.x)	xx (xx.x)	xx (xx.x)
Number of Serious TEAEs	xx	xx	xx
Treatment-Related Serious TEAE	xx (xx.x)	xx (xx.x)	xx (xx.x)
Number of Treatment-Related Serious TEAEs	xx	xx	xx
TEAE Leading to Death	xx (xx.x)	xx (xx.x)	xx (xx.x)
Number of TEAE Leading to Death	xx	xx	xx
Treatment-Related TEAE Leading to Death	xx (xx.x)	xx (xx.x)	xx (xx.x)
Number of Treatment-Related TEAE Leading to Death	xx	xx	

Note: TEAE onset is based on the start of treatment in the LTS. Adverse events were coded using MedDRA 18.1. TR=Treatment-Related.

Source: Listing xx.x.x.x, Program: xxxxx.sas, Output: T\_xx.x\_x\_x\_x\_xxx.rtf, Generated on: DDMMMYYYY HH:MM

Protocol Number: NI-AC303

Table 14.3.3.2.1

Treatment Emergent Adverse Events (TEAE) by System Organ Class, Preferred Term, and Duration of Exposure Safety Population

System Organ Class Preferred Term	Within 24 hours (N=XXX)	Within 2-30 days (N=XXX)	Within 31-90 Days (N=XXX)	Within 91-180 Days (N=XXX)	Within 181-365 Days (N=XXX)	Overall (N=XXX)
Number of Subjects with at Least One TEAE Number of Events	xx (xx.x)	xx (xx.x)	xx (xx.x)	xx (xx.x)	xx (xx.x)	xx (xx.x) xx
System Organ Class 1	xx (xx.x)	xx (xx.x)	xx (xx.x)	xx (xx.x)	xx (xx.x)	xx (xx.x)
Preferred Term 1	xx (xx.x)	xx (xx.x)	xx (xx.x)	xx (xx.x)	xx (xx.x)	xx (xx.x)
Preferred Term 2	xx (xx.x)	xx (xx.x)	xx (xx.x)	xx (xx.x)	xx (xx.x)	xx (xx.x)
System Organ Class 2	xx (xx.x)	xx (xx.x)	xx (xx.x)	xx (xx.x)	xx (xx.x)	xx (xx.x)
Preferred Term 1	xx (xx.x)	xx (xx.x)	xx (xx.x)	xx (xx.x)	xx (xx.x)	xx (xx.x)
Preferred Term 2	xx (xx.x)	xx (xx.x)	xx (xx.x)	xx (xx.x)	xx (xx.x)	xx (xx.x)

Note(s): Adverse event terms were coded using MedDRA dictionary version 18.1. Subjects are counted once within each level of summary. Duration of exposure is based on date of first dose of SB204, which could be in the previous study (NI-AC301 or NI-AC302).

Source: Listing xx.x.x.x, Program: xxxxx.sas, Output: T xx.x x x xxxx.rtf, Generated on: DDMMMYYYY HH:MM

Programmer Note: Order SOC by decreasing frequency and preferred term by decreasing frequency within SOC based on overall incidence.

Protocol Number: NI-AC303

Table 14.3.3.2.2

Treatment Emergent Adverse Events (TEAE) by System Organ Class, Preferred Term, and Extent of Exposure Safety Population

System Organ Class Preferred Term	1-100 grams (N=XXX)	>100-330 grams (N=XXX)	>330-675 grams (N=XXX)	>675 Grams (N=XXX)	Overall (N=XXX)
Number of Subjects with at Least One Event	xx (xx.x)	xx (xx.x)	xx (xx.x)	xx (xx.x)	xx (xx.x)
Number of Events	xx	xx	xx	xx	xx
System Organ Class 1 Preferred Term 1 Preferred Term 2	xx (xx.x)	xx (xx.x)	xx (xx.x)	xx (xx.x)	xx (xx.x)
	xx (xx.x)	xx (xx.x)	xx (xx.x)	xx (xx.x)	xx (xx.x)
	xx (xx.x)	xx (xx.x)	xx (xx.x)	xx (xx.x)	xx (xx.x)
System Organ Class 2 Preferred Term 1 Preferred Term 2	xx (xx.x)	xx (xx.x)	xx (xx.x)	xx (xx.x)	xx (xx.x)
	xx (xx.x)	xx (xx.x)	xx (xx.x)	xx (xx.x)	xx (xx.x)
	xx (xx.x)	xx (xx.x)	xx (xx.x)	xx (xx.x)	xx (xx.x)

Note(s): Adverse event terms were coded using MedDRA dictionary version 18.1. Subjects are counted once within each level of summary. TEAE onset is based on the start of treatment in the LTS. Extent of exposure is based on first exposure to SB204 - which could be in the previous study (NI-AC301 or NI-AC302).

Source: Listing xx.x.x.x.x, Program: xxxxx.sas, Output: T xx.x x x xxxx.rtf, Generated on: DDMMMYYYY HH:MM

Programmer Note: Order SOC by decreasing frequency and preferred term by decreasing frequency within SOC based on overall incidence.

Protocol Number: NI-AC303

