#### 3.5 Populations

#### 3.5.1 Safety Population

The safety population (SAF) will include all subjects that have received at least one dose of SB204. For the summaries, we are defining two subject categories, based on the subject's status at the start of the LTS:

- SB204 Experienced: subjects allocated to SB204 in the previous study
- SB204 Naïve: subjects allocated to vehicle in the previous study

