### 4.4 Extent and Duration of Exposure

Summaries of the duration of exposure, days of exposure, and extent of exposure (calculated total grams) to study drug will be presented, overall and by whether previously randomized to SB204 (SB204 experienced) or randomized to Vehicle (SB204 naïve). This information plus study drug management details will be listed as well. All exposure endpoints will take into account whether the subject received SB204 in the previous study (NI-AC301 or NI-AC302).

Duration of exposure will be defined as:

Date of Last Drug Administration – Date of First Drug Administration + 1 day

Where date of first drug administration is the date of first treatment in the previous pivotal study for subjects randomized to SB204 in the previous study, and date of first dose in the LTS for subjects randomized to vehicle in the previous study.

Days of exposure will be defined as the total number of days that the subject reported taking study medication, and includes the days of exposure to SB204 in the previous study (NI-AC301 or NI-AC302) if applicable.

Extent of exposure will be based on the number of areas treated (face, upper back, and/or upper chest/shoulders, and any other areas reported) and the number of days with treatment. For subjects randomized to SB204 in the previous studies, drug was only applied to the face so for the days of exposure from the previous studies, it will be assumed that there is only one area of application, i.e. the face.

Each application is equal to 0.9 g. Extent of exposure is estimated as the sum of application areas (face only=1, face and chest=2, etc.) times the number of days of application to those areas times 0.9g. For example, a subject who applies 200 applications to the face only will have extent of exposure = 180g, while a subject who applies 100 applications to the face and 50 applications to the upper back will have extent of exposure = 135 g. The maximum extent of exposure would be: [0.9 grams x number of days on treatment in previous study] + [0.9 grams x 4 areas x number of LTS days on treatment]. Most subjects will have less exposure than this, so extent of exposure will be categorized logically depending on actual distribution of subjects. Initially, quartiles will considered.

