#### 4.5.4 Vital Signs

Blood pressure and pulse will be summarized from Baseline through Week 40/ET. Additionally, change from Baseline in vital signs will be summarized at Week 4, 12, 24, 36, and 40/ET. Clinically significant changes from Baseline will be documented as an AE.

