### 4.6 Tolerability

Distribution and shift in cutaneous tolerability assessments (erythema, scaling, dryness, pruritus, burning/stinging) will be summarized from Baseline to Week 40/ET.

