### 4.7 Efficacy Analysis

The facial area inflammatory and non-inflammatory lesion counts will be summarized at each evaluation from Baseline through Week 40/ET. Absolute and percent change in inflammatory and non-inflammatory lesion counts will be summarized at Weeks 4, 12, 24, 36 and 40/ET. The absolute and percent change in inflammatory non-inflammatory lesion counts will also be summarized by prior treatment (SB204 experienced, SB204 naïve).

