#### <Parameter> (<units>)

	-	SB204
		N=XXX)
Timepoint	Actual	Change from Baseline
Baseline		
n	XX	
Mean (SD)	xx.x (xx.xx)	
Median	XX.X	
Min, Max	XX, XX	
Missing	xx	
Week 4		
N	XX	XX
Mean (SD)	xx.x (xx.xx)	xx.x (xx.xx)
Median	XX.X	XX.X
Min, Max	xx, xx	XX, XX
Missing	xx	XX
Week 12		
n	XX	XX
Mean (SD)	xx.x (xx.xx)	xx.x (xx.xx)
Median	XX.X	XX.X
Min, Max	xx, xx	xx, xx
• • • •		XX

Note(s): Baseline is defined as the Week 12 assessment from the previous study (NI-AC301 or NI-AC302). Source: Listing xx.x.x.x, Program: xxxxx.sas, Output: T\_xx.x\_x\_x\_xxxx.rtf, Generated on: DDMMMYYYY HH:MM

Programmer Note: Include all vital signs parameters (e.g. SBP, DBP, Pulse) and all available post-baseline visits. Missing not presented if no missing values.

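### Tolerability and vital-sign tables pool SB204-experienced and SB204-naïve subjects, so a lasting change after the switch from vehicle to SB204 can be diluted

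*SAP*

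**What the plan says.** Protocol 3.2 admits completers of NI-AC301 or NI-AC302 from either arm. SAP 3.5.1 then sorts them: "For the summaries, we are defining two subject categories", namely SB204 Experienced (SB204 in the pivotal study) and SB204 Naïve (vehicle in the pivotal study).

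Baseline is the pivotal Week 12 value for everyone. The footnotes to Tables 14.3.1.1 and 14.3.2.1 say "Baseline is the Week 12 assessment from the previous study (NI-AC301 or NI-AC302", and the footnote to Table 14.3.4 says "Baseline is defined as the Week 12 assessment from the previous study (NI-AC301 or NI-AC302".

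The two categories appear as columns for demographics (14.1.2.1), adverse events ongoing at entry (14.1.4), exposure (14.2.1) and Table 14.3.3.1, the "Treatment Emergent Adverse Events (TEAE) Overview". For lesion counts, SAP 4.7 says changes "will also be summarized by prior treatment", and Tables 14.2.3.x do so.

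No split is named for tolerability or vital signs. SAP 4.6 plans "Distribution and shift in cutaneous tolerability assessments" from Baseline to Week 40/ET. SAP 4.5.4 says "change from Baseline in vital signs will be summarized at Week 4, 12, 24, 36, and 40/ET". The shells for 14.3.1.x and 14.3.4 have a single SB204 column, and 14.3.2.x is cross-classified by Baseline score only.

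**The concern.** The two categories start from different treatment states. A naïve subject's change from Baseline is a move from vehicle to SB204. An experienced subject's change is a move from about 12 weeks of SB204 to more SB204. A reaction already present at Week 12 in experienced subjects cannot show as a change in them, so averaging the two groups pulls the result towards zero.

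Protocol 1.5 links topical application to erythema, scaling, dryness and burning/stinging, and lists hypotension as a theoretical risk. These tables therefore cover effects that the protocol itself expects or watches for.

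Under Protocol 4.2 a tolerability score becomes an adverse event only if it is severe or leads to discontinuation. Mild and moderate scores otherwise never reach the split TEAE overview, so the tolerability displays are where they are summarized. A reader could take a small pooled shift as reassurance about starting SB204 when many of the subjects had started 12 weeks earlier.

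**Working it through.** The plan has no figure to reproduce: SAP 3.6 and Protocol 7.9 say no sample size or power calculation was done.

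**Step 1: exposure at Baseline and afterwards.**

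| | Experienced | Naïve |
|---|---|---|
| Baseline (pivotal Week 12) | on SB204 | on vehicle |
| Week 4 to Week 40 | SB204 | SB204 |
| New to SB204 on the face | no | yes |

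For pivotal exposure SAP 4.4 states "For subjects randomized to SB204 in the previous studies, drug was only applied to the face". It counts the face as one 0.9 g application in both studies, and tolerability is scored on the face only. For the face, then, only the naïve group changes treatment at entry. For vital signs the contrast is less clean, because experienced subjects may also extend treatment to the back, chest or shoulders.

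**Step 2: dilution.** Let f be the experienced share and r the experienced change as a fraction of the naïve change. Then

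pooled change / naïve change = (1 − f) + f × r.

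The documents give neither f nor r. With f assumed at 1/3, 1/2 or 2/3, and r = 0 (no further change in experienced subjects):

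- f = 1/3: 1 − 0.333 = 0.67
- f = 1/2: 1 − 0.500 = 0.50
- f = 2/3: 1 − 0.667 = 0.33

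If r = 1 the ratio is 1 and nothing is diluted.

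**Step 3: an example with assumed rates.** Suppose 10% of naïve subjects shift to a worse erythema score.

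| Experienced shifting | f = 1/3 | f = 1/2 | f = 2/3 |
|---|---|---|---|
| 0% | 6.7% | 5.0% | 3.3% |
| 2% | 7.3% | 6.0% | 4.7% |
| 10% | 10% | 10% | 10% |

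For instance, with 2% and f = 1/2: 0.5 × 10 + 0.5 × 2 = 6.0%.

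**Step 4: which displays this fits.** Table 14.3.4 prints a mean change, so the ratio applies to it directly. Tables 14.3.2.x print cells, so the ratio applies only to an overall proportion obtained by summing cells. It does not apply within one Baseline-score column, where the mix depends on how many subjects of each group had that score. Tables 14.3.1.x print no change. There, dilution affects only a reader's comparison of the Baseline rows with later rows; the post-baseline distributions themselves are not diluted.

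**Step 5: precision after a split.** For 400 to 200 naïve subjects out of 600 (the same assumed shares), the standard error grows by √(600/400) = 1.22 to √(600/200) = 1.73. For an assumed 10% proportion, the 95% half-width 1.96 × √(0.1 × 0.9 / n) is 2.9 points (n = 400) to 4.2 points (n = 200), against 2.4 points (n = 600).

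**The case against.** The other side has a good deal that stands.

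- **It is a display choice.** The objective is safety for up to 40 weeks, not a contrast of vehicle with first use. Protocol 7.5.3 and 7.6 ask for no split, and TEAEs by severity, medical history and concomitant medications are pooled too. A reader might infer that SAP 3.5.1 commits every summary to the two categories. It does not say which summaries, so the shells do not contradict it.
- **A split would not reveal early reactions.** A reader might infer that first-exposure effects in general are being hidden. The first post-baseline visit is Day 28 ± 5. The flushing described in Protocol 1.5 lasts roughly 5 to 10 minutes, and tolerability is scored at least 30 minutes after application. Pruritus and burning/stinging cover only the previous 24 hours. Reactions that resolve before Week 4 are missed by these tables in either layout.
- **No further change is an assumption, not a bound.** Protocol 3 lets treatment stop in remission and restart, and Protocol 3.6 admits subjects whose faces have cleared. Protocol 1.5 also says the vehicle may cause local reactions, so naïve subjects may already carry some at Baseline.
- **Vital signs are the weaker limb.** Hypotension is only a theoretical risk. The pharmacokinetic study in Protocol 1.4, at 8% on about 17% BSA, found no detectable hMAP3 and no nitrate difference from vehicle. Clinically significant changes become adverse events and reach the split overview. A reader might scale the vital-sign dilution by grams applied, but nothing in the documents supports an effect proportional to amount.
- **The figures may already help.** Figures 14.1.1 to 14.1.5 are titled by treatment and visit. The images are not shown, and the grouping may be prior treatment.

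These points limit the size and reach of the concern but do not remove it. Even if split, the figures would cover score distributions, not shifts or vital signs. Listings 16.2.7.3 and 16.2.7.4 give the previous study but not the previous arm, so a reader would have to merge them with Listing 16.2.1.1.

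**Conclusion.** The concern holds in a limited form. The three sets of tables pool subjects whose Baselines were taken on different treatments. A change that follows the switch from vehicle to SB204 and persists to a scheduled visit is diluted whenever experienced subjects change less than naïve subjects. The case is strongest for the facial shift tables, because mild or moderate scores without discontinuation do not become adverse events, and weaker for vital signs.

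The size cannot be fixed from the documents. The range 0.67 to 0.33 rests on an assumed experienced share of 1/3 to 2/3 and on no further change in that group; smaller differences between the groups give less dilution. The documents do not support calling this an error or a breach of the plan. It is a cheap improvement, and medium confidence is appropriate.

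**What to change.** Keep Week 12 as Baseline, and:

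1. Give Tables 14.3.1.x and 14.3.4 the columns SB204 Experienced, SB204 Naïve and Overall, as in Table 14.2.1.
2. Give the shift Tables 14.3.2.x one panel for each of the three.
3. Add to SAP 4.5.4 and 4.6: *Results will be presented overall and by prior treatment (SB204 experienced, SB204 naïve).*
4. Add a footnote that the naïve columns show an uncontrolled change from vehicle to SB204.

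Prior treatment is already planned data (SAP 4.3, Listing 16.2.1.1), so nothing new is collected, and keeping Overall means no planned result is lost. The cost is pages and sparse cells. The shift tables hold 5 signs × 5 visits × 25 cells = 625 cells, and three panels make 1,875. Naïve estimates would be 1.22 to 1.73 times less precise than pooled ones under the shares assumed above.

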7.5 SAFETY

7.5.1 ADVERSE EVENTS

All AEs that occur during the study or continue after enrollment into this study will be recorded and classified on the basis of MedDRA terminology. Treatment-emergent adverse events (TEAEs) are defined as AEs reported on or after the first day of enrollment in this long term safety study.

All information pertaining to an AE noted during the study will be listed by subject, detailing verbatim term given by the PI or designee, preferred term, system organ class (SOC), onset date, resolution date, severity, seriousness, action taken, outcome, and drug relatedness. The event onset will also be shown relative (in number of days) to date of first dose in this study.

Treatment-emergent AEs will be summarized by the number of subjects reporting a TEAE, SOC, preferred term, severity, relationship to study drug (causality), and seriousness. When summarizing AEs by severity and relationship, each subject will be counted only once within a system organ class or a preferred term by using the event with the highest severity and greatest relationship within each classification.

Adverse events will also be summarized by windows of exposure to study drug. The windows will include but are not limited to: 1) within the first 24 hours of exposure, 2) up to 1 month of exposure, 3) up to 3 months of exposure, 4) up to 6 months of exposure and 5) up to 12 months of exposure.

AEs will also be summarized based on extent of exposure as described in Section 7.7

Serious AEs will be summarized by severity, and relationship to study drug, and individual SAEs will be listed by subject. In addition, a list of subjects who prematurely discontinue from the study due to an AE will be provided.

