## 4 Statistical Methodology

#### 4.1 Planned Analyses

All statistical processing will be performed using statistical analysis software (SAS®) unless otherwise stated. Safety analyses will be performed using the safety population.

Continuous data will be summarized with sample size (N), mean, median, standard deviation, minimum and maximum. Categorical data will be summarized with N, frequency counts, and percentages, based on N.

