#### 4.5 Safety

#### 4.5.1 Adverse Events

All AEs that occur during the study or continue after enrollment into this study will be recorded and classified on the basis of Medical Dictionary for Regulatory Activities (MedDRA) terminology version 18.1. Adverse events ongoing at end of the pivotal study will be carried forward to this study, will not be considered treatment-emergent for this study, and will be summarized separately by SOC, PT, and relatedness. Treatment-emergent AEs (TEAEs) will be defined as AEs reported on or after the first day of enrollment in this long term safety study.

All information pertaining to an AE noted during the study will be listed by subject, detailing verbatim term given by the Investigator or designee, preferred term, system organ class (SOC), onset date, resolution date, severity, seriousness, action taken, outcome, and drug relatedness. The event onset will also be shown relative (in number of days) to date of first dose in this study.

Treatment-emergent AEs will be summarized by the number of subjects reporting a TEAE, SOC, preferred term, severity, relationship to study drug (causality), and seriousness. When summarizing AEs by severity and relationship, each subject will be counted only once, within a system organ class or a preferred term, by using the event with the highest severity and greatest relationship within each classification.

Serious AEs will be summarized by severity, and relationship to study drug, and individual SAEs will be listed by subject. In addition, a list of subjects who prematurely discontinue study drug due to an AE, had AEs leading to treatment modification, and AEs that resulted in death will be provided.

Adverse events will also be summarized by windows of duration of exposure to study drug to determine if there is a safety signal due to duration of exposure. The windows of exposure will include but are not limited to: 1) within the first 24 hours (i.e. Day 1 of the LTS study), 2) up to 1 month (i.e. 2-30 days), 3) up to 3 months (i.e. 31-90 days), 4) up to 6 months (i.e. 91-180 days) and 5) up to 12 months (i.e. 181-365 days).

Adverse event incidence will also be summarized by the extent of exposure categories (in grams) as described in section 4.4.

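### The AE-by-duration tables count only LTS-onset events on a first-ever-dose clock, pool experienced with naïve subjects and leave N undefined, so percentages before exposure day 91 can print too low

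*SAP*

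**What the plan says.** - **Events counted.** SAP 4.5.1: "Treatment-emergent AEs (TEAEs) will be defined as AEs reported on or after the first day of enrollment in this long term safety study". Pivotal-study events still ongoing at entry are tabulated separately and are not treatment-emergent.
- **Clock.** In SAP 4.4 exposure starts at "the date of first treatment in the previous pivotal study for subjects randomized to SB204 in the previous study", and at the first LTS dose for subjects previously on vehicle. The footnote to Table 14.3.3.2.1 agrees: "Duration of exposure is based on date of first dose of SB204, which could be in the previous study (NI-AC301 or NI-AC302". The footnote to Listing 16.2.8.1 uses the same origin.
- **Windows.** SAP 4.5.1 lists day 1, days 2–30, 31–90, 91–180 and 181–365, introduced by "The windows of exposure will include but are not limited to". It glosses the first as "within the first 24 hours (i.e. Day 1 of the LTS study". Protocol 7.5.1 has only "within the first 24 hours of exposure", with no LTS origin, and the later windows name none.
- **Layout and denominator.** The shell has one column per window plus an overall column. Each carries an N placeholder that is not defined, and there is no split by prior treatment. The shell is reused through Table 14.3.3.11.1, which makes ten duration tables. SAP 4.1 gives the general rules: "Safety analyses will be performed using the safety population" and "Categorical data will be summarized with N, frequency counts, and percentages, based on N".
- **Subgroups.** SAP 3.5.1 defines SB204-experienced and SB204-naïve subjects for use in summaries. Table 14.3.3.1 uses the split for TEAE totals; no TEAE table by system organ class and preferred term does.

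**The concern.** The numerator opens at LTS enrolment. For experienced subjects the exposure clock has by then run for about twelve weeks. The early windows are empty for them by construction, yet nothing removes them from the denominators of those windows.

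SAP 4.5.1 says these tables are meant to show whether a safety signal depends on duration of exposure. If experienced subjects stay in N, a reaction typical of the first weeks of use prints too low in the columns meant to reveal it. A row of zeros would also look better supported than it is.

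Separately, the gloss on window 1 conflicts with the footnote clock, so two programmers could file the same event in different columns.

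**Working it through.** The documents give no adverse event percentage, so there is no plan figure to reproduce. The check is day counting, followed by an illustration.

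**1. Entry day.** Exposure day = date − date of first dose + 1 (SAP 4.4). Assume the first pivotal dose on pivotal Day 0 and the Week 12 visit on Day 12 × 7 = 84; the pivotal visit window is not in the documents. Protocol 3.5 allows an entry gap g of 0 to 7 days. An experienced subject then enters on exposure day 84 + g + 1 = 85 + g, that is 85 to 92.

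**2. Last day.** Week 40 is Day 280 from Baseline. A naïve subject with no gap is observed on exposure days 1 to 281. For an experienced subject, if visits are timed from the pivotal Week 12 visit, nominal Week 40 is day 85 + 280 = 365.

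**3. LTS-observed days per window, first-ever-dose clock.** For days 31–90 an experienced subject has max(0, 6 − g) days.

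| Window | Naïve, no gap | Experienced, g = 0 | Experienced, g = 7 |
|---|---|---|---|
| Day 1 | 1 of 1 | 0 of 1 | 0 of 1 |
| 2–30 | 29 of 29 | 0 of 29 | 0 of 29 |
| 31–90 | 60 of 60 | 6 of 60 | 0 of 60 |
| 91–180 | 90 of 90 | 90 of 90 | 89 of 90 |
| 181–365 | 101 of 185 | 185 of 185 | 185 of 185 |

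The naïve shortfall in the last row comes from study length, not from the clock.

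**4. Printed percentage when N includes experienced subjects.** Let s be the naïve share (not in the documents; assumed 1/3 to 2/3) and r the naïve risk in the window (assumed 10% for illustration).
- Days 2–30: printed = s × r. For s = 1/3, 1/2, 2/3 this is 3.3%, 5.0%, 6.7%.
- Days 31–90, with the same constant daily rate in both groups: rate = −ln(0.9)/60 = 0.00176. With d observed days, the experienced risk is 1 − exp(−rate × d), which is 1.05% for d = 6 and 0 for d = 0. Printed = s × 10% + (1 − s) × experienced risk. For s = 1/3, 1/2, 2/3 this is 4.0%, 5.5%, 7.0% (d = 6) or 3.3%, 5.0%, 6.7% (d = 0).

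**5. A zero row in days 2–30.** The one-sided 95% upper bound for no events in n subjects is 1 − 0.05^(1/n). With n = 600 it is 0.50%. On the assumed share only 200 to 400 subjects could contribute; for them the bound is 1.49% to 0.75%.

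**6. Window 1.** There are two readings.
- *Footnote clock:* experienced subjects have 0 of 1 day, so the column is diluted exactly as days 2–30 are.
- *SAP 4.5.1 gloss:* every subject is observed on LTS Day 1. But an experienced subject's event that day falls at about exposure day 85 to 92. It is filed as a first-24-hour event and also meets the 31–90 window (g = 0 to 5) or the 91–180 window (g = 6 or 7). No rule says which column takes it.

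**The case against.** **The denominator is open.** Each window has its own N placeholder, which could be meant as the number under LTS observation in that window. There would then be no dilution. This stands: the dilution is conditional, and a reader who takes it as certain goes further than the documents do. But no passage states that restriction. The only written default is the safety population, and the other natural reading, everyone who passed through the window, also includes the experienced subjects, who did so in the pivotal study.

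**Window 1 cannot have both faults.** A reader might infer that it is both diluted and mislabelled. It has one fault or the other, depending on which passage governs.

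**One LTS clock throughout would remove the dilution.** True, but that contradicts SAP 4.4 and both footnotes, and it would mix first use with continued use. The 365-day limit also fits the first-ever-dose clock (84 + 280 = 364 treatment days); an LTS clock would end near day 281.

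**The stakes are limited.** The objective is long-term safety, and the windows from day 91 are largely sound. Protocol 4.2 keeps erythema, scaling, dryness, pruritus and burning/stinging out of AE reporting unless severe or leading to discontinuation, so most local reactions appear in the tolerability tables. Table 14.3.3.1 splits the totals, and Listing 16.2.8.1 allows later recovery. All of this stands and limits the importance of the point.

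**Overrun of the last window.** A reader might infer that follow-up reaches exposure day 379. That needs visits to be timed from enrolment (365 + 7 + 7). Protocol 3.3, 3.5 and the footnotes to Table 2 make the pivotal Week 12 visit the Baseline and time visits from it, which gives day 365 nominally and 372 with the +7-day visit window.

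**Conclusion.** The point holds and should be fixed before the tables are produced. The mismatch between an LTS-onset numerator and a first-ever-dose clock is plain in the text. At nominal timing, experienced subjects have no countable day in days 2–30 and 0 to 6 of 60 in days 31–90; the unseen pivotal visit window could shift the latter by a few days.

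If N is the safety population, or everyone who passed through the window, the days 2–30 percentage equals the naïve risk times the naïve share, and days 31–90 nearly so. The 3.3% to 7.0% range for a 10% risk rests on an assumed risk and an assumed share, so it shows direction rather than expected size. The 200 to 400 subjects behind the zero-event bounds rest on the same assumed share.

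The documents do not support a claim that dilution is certain, that the later windows are compromised, or that early local reactions go unseen.

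**What to change.** 1. Reconcile SAP 4.5.1 with SAP 4.4 and the footnotes so that all windows use one clock. If that is the first-ever SB204 dose, as SAP 4.4 and both footnotes state, delete the gloss tying window 1 to LTS Day 1.
2. State in SAP 4.5.1 and the shell footnote that each column's N is the number of subjects under LTS adverse event observation in that exposure window. This alone removes the dilution.
3. Show the SAP 3.5.1 experienced/naïve split at least in Tables 14.3.3.2.1 (all TEAEs) and 14.3.3.3.1 (treatment-related). Where a group has no observed days, print *not observed* instead of zero. The sparser tables, such as those for deaths, need not be split.
4. Optionally, make the last window open-ended (>180 days), since exposure can reach about day 372 with the Week 40 visit window. SAP 4.5.1 already allows further windows.

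The cost is SAP wording, footnotes and modest programming. No new data are needed: SAP 4.4 already uses the pivotal first-treatment date, and Listing 16.2.8.1 carries first dose and event start dates. The downside is longer tables and some small cells, above all experienced subjects in days 31–90.
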